#### Changes due to the impact of COVID-19:

We anticipate that the weekly number of admissions will return to baseline over the next 2-3 months. Therefore, Phase I will be split into baseline data collation during a pandemic period (first 3 months), and non-pandemic period (latter 3 months)

**Control Site (Phase I, 12 months):** Kiambu County Referral Hospital in Nairobi, Kenya will serve as the control site and no intervention will be implemented. At this site, Phase I will commence for a period of 12 months. There will be no Phase II or Phase III.

Phase II (1-3 months) will involve technology development, usability testing, and training.

**Phase IIa: Technology Development.** A risk prediction model will be derived using the data collected in Phase I and implemented in a Digital Triaging Platform, along with a digitized version of the ETAT+ guidelines. The Digital Triaging Platform, including vital sign measurement devices (PhoneOx [10] and RRate [11]) and the mobile application and clinical dashboard [12][13][14] has already been developed and evaluated. Once the digital triage tool has been developed, it will be evaluated in potential users using simulated patient scenarios and a 'Think Aloud' method.

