#### Selected Sample size

Based on the uncertainty commonly present in these smaller sample sizes [20], the desire to include the possibly of modelling non-linearities in our models (using machine learning methods) and the clinical feasibility (large case load) we plan to target a larger sample of 4000 at each site, with a minimum sample size of 1000 participants enrolled in Phase I. Based on the activity at our selected sites this would require no more than a 60% recruitment rate during a sixmonth period.

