### Changes due to the impact of COVID-19:

We hypothesize that the case mix of the "pandemic period" cohort is likely to be different to the case mix seen during "non-pandemic" times. This includes a potential increase in the average severity of disease in those children presenting at the facility. We are requesting support for the addition of a pandemic phase in Phase 1 – the baseline observational component of PRST. This will include a 25% increase in sample size at each experimental site (250 additional participants per experimental site). This increase in sample size is critical to developing a risk stratification model that is robust during pandemic and non-pandemic times.

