#### **Outcomes Analysis**

We will compare the proportion of children at the two intervention sites receiving a completed bundle within 60 minutes to the historical and the contemporaneous control group (Marascuillo procedure). The median time to an appropriate bundle of care will be compared using a Mann–Whitney U test. The triage prioritization between the phases and the proportion of children who received and appropriate bundle of care within each triage categorization will be compared with Fisher's exact tests. Segmented regression analysis of the interrupted time series of the pre- and post- intervention periods will be used to assess immediate effects and effects over time, controlling for prior trends that may continue without our intervention. Quantile regression will be used to estimate the median differences. We will compare the estimated times at end of the intervention period with the expected counterfactual value, had the pre-intervention trend continued as if the intervention never occurred. We will compare the time to event (treatment bundle) using the Kaplan-Meier estimator with censure at 180 minutes. Secondary outcomes will be compared using generalized estimating equations.

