#### Additional Analyses due to the impact of COVID-19:

# Develop data driven prediction models for identifying vulnerable children with suspected sepsis that are robust during future COVID-19 surges and novel pandemics.

We will specifically look at the predictive performance of the model during this initial pandemic period (2-3 months) in comparison to following non-pandemic period. We will use traditional statistical modeling techniques (e.g. logistic regression) and data-driven algorithms (e.g. elastic net and random forest) to identify new predictors and calibrate existing predictors, exploring possible interactions between periods. We will validate the model using test sets that include both post-and during-pandemic data in order to ensure that any newly derived model performs consistently during both periods. Performance of prediction models will rely on area under receiver operating characteristics, and specificity corresponding to 80% sensitivity. Our goal is to develop a model for identifying those most at risk for sepsis that performs well despite changes in case mix of our cohort, even if this slightly degrades overall prediction performance. This will ensure that the final model will be more robust to future changes in case mix during future health crises.

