# Identify the variables that contribute to vulnerability in children with suspected sepsis, during pandemic and non-pandemic times.

We will use descriptive statistics and standard statistical tests to compare the clinical, demographic and social factors of the pre-pandemic and pandemic cohorts. These include important identity factors such as gender, age, economic indicators, and geography. Multivariate models such as clustering algorithms and Principal Component Analysis will be used to further understand if and how the pre-and during-pandemic cohorts separate and differ.

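### The pandemic/non-pandemic split of the baseline is not carried into the effectiveness analyses: the pre/post tests are unadjusted, and a projected baseline trend could turn a shift inside Phase I into an apparent tool effect

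*Combined protocol and SAP*

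**What the plan says.** Section 17 of protocol Version 5.0 (Outcomes Analysis) lists several effectiveness analyses and labels none of them primary. The proportion treated within 60 minutes is compared with an earlier and a concurrent control group by the Marascuilo procedure. Median times are compared by a Mann-Whitney test, and triage categories by Fisher's exact test. There is also a Kaplan-Meier comparison. None of these is given covariates. A segmented regression is meant to allow for trends already under way, and its end-of-period contrast is this: "We will compare the estimated times at end of the intervention period with the expected counterfactual value, had the pre-intervention trend continued". The shape of the trend is not stated, nor whether the model has a term for the pandemic months.

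Section 7 divides the baseline: "Therefore, Phase I will be split into baseline data collation during a pandemic period (first 3 months), and non-pandemic period (latter 3 months". The reason given is that "We anticipate that the weekly number of admissions will return to baseline over the next 2-3 months". Section 13 expects case mix to differ in the pandemic part: "This includes a potential increase in the average severity of disease in those children presenting at the facility".

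Section 17 uses the split in two places, both outside the effectiveness analysis. One is the performance of the prediction model "during this initial pandemic period (2-3 months) in comparison to following non-pandemic period". The other is a description intended to "compare the clinical, demographic and social factors of the pre-pandemic and pandemic cohorts". The three descriptions of the split do not match: first three months, two to three months, and a pre-pandemic cohort where section 7 puts the pandemic cohort first.

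At the end of section 7, study nurses continue to collect the predictor variables in Phase III so that the two cohorts' characteristics can be compared.

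**The concern.** The comparison is not randomised, and the plan itself expects volume and severity to move inside the baseline. Both could plausibly affect how long a child waits. Two things follow.

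- Tests without covariates cannot separate a change in who attends from a change caused by the tool, although the predictors needed for adjustment are collected in both phases.
- A straight trend through a baseline containing a completed shift treats that shift as continuing change and carries it to the end of Phase III. A tool with no effect could then look helpful or harmful, and a real benefit could be hidden, depending on the direction of the shift.

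If the handling and the boundary are left open, they can also be settled after outcomes are seen.

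**Working it through.** The plan gives no figure on this point to reproduce, so the check is of the mechanism.

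**Inputs from the protocol.** Baseline 6 months, taken as 26 weeks, with the nominal change after week 13 (section 7). Phase II lasts 1 to 3 months, taken as a gap of 4 or 13 weeks (section 7). Phase III is 26 weeks (six months in the updated timeline).

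**Assumptions.** The tool has no effect. One straight baseline trend is fitted, with equal weekly weights. Time to treatment differs by D, the non-pandemic level minus the pandemic level, and the shift is complete by week 13. D is not in the documents.

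**Formula.** Let y(t) be the baseline series in units of D, with the settled level at 0. For a recovery over r weeks, y = min(t/r, 1) − 1. For a step, y = −1 to week 13, then 0. Least squares on t = 1 to 26 has mean week 13.5 and Sxx = 26(26² − 1)/12 = 1462.5. The projection at week T is mean(y) + slope × (T − 13.5). The true value is 0, so the projection is the spurious effect. With D positive it appears as a reduction in time.

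**Step case.** mean(y) = −13/26 = −0.500. Σ(t − 13.5)y = 175.5 − 91 = 84.5, so slope = 84.5/1462.5 = 0.0578. At T = 56 (26 + 4 + 26): −0.500 + 0.0578 × 42.5 = 1.96.

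**All shapes, in units of D**

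| Shift | mean(y) | slope | Go-live, 4-week gap (T=31) | End, 4-week gap (T=56) | Go-live, 13-week gap (T=40) | End, 13-week gap (T=65) |
|---|---|---|---|---|---|---|
| 8-week recovery | −0.135 | 0.0251 | 0.31 | 0.93 | 0.53 | 1.16 |
| 13-week recovery | −0.231 | 0.0362 | 0.40 | 1.31 | 0.73 | 1.64 |
| Step after week 13 | −0.500 | 0.0578 | 0.51 | 1.96 | 1.03 | 2.48 |

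A closed form in months agrees for the step. The slope is 0.25D per month, so the projection at month 13 is 0.5D + 0.25D × 10 = 3D against a true 1D, an excess of 2D. With a 4-week gap and a 13-week Phase III (T = 43), the end-of-period values are 0.61D, 0.84D and 1.20D.

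**Pooled baseline mean.** With equal weekly weights it is off by 0.13D, 0.23D and 0.50D. Section 13 plans Phase I "with a minimum sample size of 1000 participants enrolled in Phase I" plus 250 more per experimental site. If pandemic children are 250 of 1,250 (a reading, since the pandemic cohort is not sized), the figures are 0.05D, 0.09D and 0.20D. On that weighting the end-of-period values with a 4-week gap become 0.68D, 1.01D and 1.76D.

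**Cost of a period term.** Giving pandemic months their own level and slope leaves weeks 14 to 26 to set the projection (mean week 20, Sxx = 13 × 168/12 = 182). Errors are taken as independent with equal weekly variance. The fitted Phase III value at its first or last week contributes 1/26 + 12.5²/1462.5 = 0.145.

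- Level change, 4-week gap, pooled: √(1/26 + 17.5²/1462.5 + 0.145) = 0.63 weekly SDs.
- The same with the period term: √(1/13 + 11²/182 + 0.145) = 0.94.
- Level change, 13-week gap: 0.82 pooled, √(1/13 + 20²/182 + 0.145) = 1.56 with the term.
- End of period, 4-week gap: 1.19 pooled, 2.71 with the term.

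**When the term does harm.** Suppose the boundary is week 13 but the step comes after week 17. Over weeks 14 to 26, mean(y) = −4/13 and slope = 18/182. At T = 56 this gives −0.308 + 0.0989 × 36 = 3.25D, against 1.57D pooled. At T = 31 it is 0.78D against 0.26D. A level-only term with an 8-week recovery gives 1.385D at T = 56, against 0.933D pooled.

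**The case against.** The case for leaving the plan alone has substance.

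- **The shift is inferred.** A reader might take the COVID-19 text to mean that waiting times will change inside the baseline. The text concerns admission numbers and a possible rise in severity. No size or sign of D is given.
- **The straight line is assumed.** A reader might infer that the plan commits to one pooled trend. It states no form, so it neither includes nor excludes a period term.
- **The projection is one analysis of several.** The Marascuilo, Mann-Whitney, Fisher and Kaplan-Meier comparisons extrapolate nothing. The published protocol paper (June 2020, before Version 5.0) makes a difference-in-differences model for treatment within one hour primary. The documents do not support saying that the effectiveness conclusion as a whole rests on the projection.
- **There is partial handling elsewhere.** The paper adds time-varying confounders as sensitivity analyses, and section 8 of Version 5.0 adds Gulu as a control. The first applies to the difference-in-differences models, for confounders that differ between groups. The second is placed in Jinja's Phase III, and in the updated timeline (table layout broken) Gulu appears to start after Jinja's baseline. Neither repairs this projection.
- **The boundary conflict is modest.** Two to three months and three months overlap, and the pre-pandemic label may be a slip.

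These points limit the weight of the concern. They do not remove the omission, or the lack of adjustment in a non-randomised comparison whose case mix the plan expects to change.

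**Conclusion.** The concern holds in a conditional form. The expected change within the baseline is not carried into the effectiveness analyses, and the pre/post tests make no use of predictors that are available in both phases. If time to treatment shifted by D and one straight pre-trend is fitted, the end-of-period projection is most exposed (about 0.9D to 2.0D with a 4-week gap, 1.2D to 2.5D with a 13-week gap). The pooled baseline mean is least exposed. As an illustration only, a D of 10 minutes would give about 9 to 20 minutes at the end of Phase III with a 4-week gap. With D equal to 0 there is no bias.

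Two further inferences should be resisted. The go-live level change is not safe: it is less exposed than the projection on the same timeline, but the 3-month interphase that section 7 allows takes its bias to 0.5D to 1.0D. Nor is a period term simply the better model, since it costs precision and can do worse than pooling if the shift comes after the boundary. This is a cheap improvement to make before outcomes are analysed; it does not show that the planned analysis is invalid.

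**What to change.** In section 17, Outcomes Analysis, before outcome data are analysed:

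1. Adjust the pre/post comparisons of the proportion treated within 60 minutes and of the median time for age and a named list of severity predictors collected by study nurses in both phases. Logistic regression with a marginal risk difference, and the quantile regression already planned, would serve. Use the study nurses' measurements and not the assigned triage category, which the tool itself may change. Section 21 starts study procedures after treatment for emergency cases, so state how their measurements are handled.
2. Add a comparison with the non-pandemic baseline months only.
3. Keep the planned segmented model. Add a pre-specified sensitivity analysis giving pandemic months their own level and slope at one calendar boundary, reconciling section 7 with the two COVID-19 paragraphs of section 17, and repeat it with the boundary moved. If results differ, interpret the end-of-period projection cautiously.

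The cost is some extra wording and analysis, with no new data. The sensitivity models are less precise: the level-change standard error rises from 0.63 to 0.94 weekly SDs with a 4-week gap, and from 0.82 to 1.56 with a 13-week gap. That, and the risk of a shift after the boundary, is why the period term is a sensitivity analysis and not a replacement. Adjustment deals only with measured case mix and cannot remove a shift caused by patient volume. If the published paper's one-month pauses in predictor collection still apply, those weeks cannot be adjusted.

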#### Additional Analyses due to the impact of COVID-19:

# Develop data driven prediction models for identifying vulnerable children with suspected sepsis that are robust during future COVID-19 surges and novel pandemics.

We will specifically look at the predictive performance of the model during this initial pandemic period (2-3 months) in comparison to following non-pandemic period. We will use traditional statistical modeling techniques (e.g. logistic regression) and data-driven algorithms (e.g. elastic net and random forest) to identify new predictors and calibrate existing predictors, exploring possible interactions between periods. We will validate the model using test sets that include both post-and during-pandemic data in order to ensure that any newly derived model performs consistently during both periods. Performance of prediction models will rely on area under receiver operating characteristics, and specificity corresponding to 80% sensitivity. Our goal is to develop a model for identifying those most at risk for sepsis that performs well despite changes in case mix of our cohort, even if this slightly degrades overall prediction performance. This will ensure that the final model will be more robust to future changes in case mix during future health crises.

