### Additional objectives due to the impact of COVID-19 at the study sites:

1. Develop data driven prediction models for identifying vulnerable children with suspected sepsis that are robust during future COVID-19 surges and novel pandemics.

- 2. Identify the variables that contribute to vulnerability in children with suspected sepsis, during pandemic and non-pandemic times.
- 3. Collect additional COVID-19 related prediction variables to inform understanding of the severity, risk factors, and clinical features of this disease at our three study sites (rural, urban and peri-urban).

**Objective B:** To validate the use of an automated Radio-Frequency Identification (RFID) method to track timeliness of interventions.

RFID tags will be small paper or plastic objects that can be attached to clothing or worn as a bracelet, anklet, or necklace (as preferred by child's caregiver) that use Bluetooth frequency band. The tag sends signals which allows tracking exactly where a patient is at a given time for analysis. For example, if a patient wearing an RFID tag enters a room, a reader in the room will detect the signal and add a timestamp for when patient was in the room. The Bluetooth frequency is no different to that used by mobile phones and is not expected to interfere with other processes in the hospital.

**Objective C:** To conduct an economic evaluation to contextualize our results for informing budgetary decisions of scaling-up Smart Triage.

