# 17. Statistical Analysis

### **Model Development**

We will develop a logistic model that will predict severe infection and sepsis in children. Akaike's Information Criterion (AIC) will be used as a summary measure to select predictors for inclusion in the model. The final selection of a model will be judged on model parsimony, availability of the predictors (with respect to resources and cost), discrimination and calibration. Bootstrapping (with replacement) will be used for internal validation. Net Reclassification Index for external (Kenya) and geographical/high malaria prevalence (Jinja) will be used for validation of the prediction model. These cohorts will allow us to optimize and re-calibrate (if required) the prediction model. Appropriate triage risk threshold selected based on data, simulation and expert opinion. The final model will be integrated into an application for use on a mobile device and electronic dashboard.

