#### Statistical analysis

#### Model development

The predictive model for severe infection and sepsis in children will be developed based on the need for hospital admission of 24 h or longer. To find the best performing, and most parsimonious model, a variety of model building techniques will be compared. These will include but are not limited to: stepwise regression based on Akaike's Information Criterion (AIC), penalized regression via elastic net, and random forest [21]. Models will be compared based on the area under the receiver operating curve, and the specificity achieved at high (80-90%) sensitivity thresholds. Models within 10% of the best performing model will be considered. Final model selection will depend on parsimony, availability of predictors across sites (based on resources, cost and feasibility of collection), discrimination and calibration. All model comparisons will take place within an internal validation resampling framework such as cross validation or bootstrapping. Risk thresholds to stratify participants into triage categories (emergency, priority, and queue) be selected based on sensitivity analysis and expert opinion. To account for geographical differences and disparities in disease prevalence (high malaria prevalence in Jinja, Uganda), we will use net reclassification improvement to optimize and re-calibrate (if required) the prediction model [22].

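### The pandemic-robustness analysis names only AUC and specificity at 80% sensitivity, which show little or nothing of a drift in calibration or triage-threshold performance between periods

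*Combined protocol and SAP*

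**What the plan says.** The COVID-19 additions to the objectives (protocol version 5.0, section 6) ask for prediction models that are "robust during future COVID-19 surges and novel pandemics". The matching analysis text is in section 17, Additional Analyses due to the impact of COVID-19. It makes four relevant statements:

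- On the comparison: "We will specifically look at the predictive performance of the model during this initial pandemic period (2-3 months) in comparison to following non-pandemic period".
- On test data: "We will validate the model using test sets that include both post-and during-pandemic data".
- On measures: "Performance of prediction models will rely on area under receiver operating characteristics, and specificity corresponding to 80% sensitivity".
- On the goal: a model that "performs well despite changes in case mix of our cohort", even at a slight cost in overall performance.

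The COVID-19 paragraph of the sample-size section expects the pandemic cohort to differ: "This includes a potential increase in the average severity of disease in those children presenting at the facility".

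The tool's operating points are set during model development. Section 17, Model Development, has: "Appropriate triage risk threshold selected based on data, simulation and expert opinion". The published protocol article, under Model development, has: "Risk thresholds to stratify participants into triage categories (emergency, priority, and queue) be selected based on sensitivity analysis and expert opinion". Both texts list calibration among the criteria for choosing the final model. Both allow recalibration, but link it to the Kenya and Jinja cohorts or to geography and disease prevalence, not to calendar period.

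**The concern.** AUC depends only on how children are ranked. Specificity at 80% sensitivity finds its own cut-off in whatever test set it is computed on. The tool in use does neither: a child's predicted risk is compared with thresholds chosen beforehand. If the level of predicted risk moves between periods while the ranking holds, the planned measures can look stable while the share of sick children above a threshold, or the share of all children flagged, changes a great deal.

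What is at stake is the conclusion on the added objective. A model could be judged consistent across periods on measures that do not register this kind of inconsistency.

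**Working it through.** **The plan's own figure.** The COVID-19 section gives no performance target or sample size of its own. The model-development figure reproduces: N = (n × 10)/I = (10 × 10)/0.12 = 833.3, stated as 833. It corresponds to 100 admissions.

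**Inputs.** From the documents: the two measures, an admission rate of 12%, 10 predictors, a minimum of 1000 in Phase I, and 250 more per experimental site for the pandemic phase. Assumed, because the documents give no values: AUC of 0.75 to 0.85, and a common score shift s of 0.25 to 0.75 SD in either direction.

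**Model.** Scores are N(0,1) in non-admitted children and N(μ,1) in admitted children, with μ = √2 × z(AUC). The cut-off is set once at 80% sensitivity in the reference period: t = μ − 0.842. In the other period all scores shift by s, so

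- sensitivity at the frozen cut-off = Φ(μ + s − t) = Φ(0.842 + s);
- specificity at the frozen cut-off = Φ(t − s).

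For AUC 0.85: μ = 1.466, t = 0.624 and reference specificity = Φ(0.624) = 73.4%. With s = −0.5, sensitivity = Φ(0.342) = 63.4%. With s = +0.5, sensitivity = Φ(1.342) = 91.0% and specificity = Φ(0.124) = 54.9%.

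| Assumed AUC | Reference sens / spec | s = −0.5 | s = +0.5 |
|---|---|---|---|
| 0.75 | 80.0% / 54.5% | 63.4% / 73.0% | 91.0% / 34.9% |
| 0.80 | 80.0% / 63.6% | 63.4% / 80.2% | 91.0% / 44.0% |
| 0.85 | 80.0% / 73.4% | 63.4% / 87.0% | 91.0% / 54.9% |

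In every row, AUC and specificity at 80% sensitivity computed within the shifted period equal the reference values. Over s = −0.75 to +0.75, frozen-threshold sensitivity runs from 53.7% to 94.4%. A simulation with 400,000 scores per class (AUC 0.80, s = −0.5) gave AUC 0.800, specificity at 80% sensitivity 63.6%, and frozen-threshold sensitivity 63.3%.

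**Pooled test sets** (AUC 0.80, s = −0.5 in one period). With a 50:50 mix, pooled AUC = 0.5 × 0.800 + 0.25 × Φ((1.190 − 0.5)/√2) + 0.25 × Φ((1.190 + 0.5)/√2) = 0.793, against 0.800. Pooled specificity at 80% sensitivity is 62.3%, against 63.6%. At that single pooled cut-off, sensitivity is 73.2% in the shifted period and 86.8% in the other. If the shifted period supplies 20% of the data, the four figures are 0.795, 62.7%, 67.6% and 83.1%.

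**Baseline risk only** (admission rate 12% to 24%, scores within each class unchanged, AUC 0.80). AUC and specificity at 80% sensitivity do not change. Observed/expected admissions become 0.24/0.12 = 2.0, and the share flagged rises from 41.6% to 46.8%. Frozen-threshold sensitivity and specificity do not change here either, so calibration has to be reported alongside them.

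**Precision by period.** The minimum per experimental site is 1000 + 250 = 1250. Half of this is 625, and 625 × 0.12 = 75 admissions. The 95% half-width on 80% sensitivity is 1.96 × √(0.16/75) = 9 points. The 250 additional children alone give 30 admissions and ±14 points. One month of six gives about 25 admissions and ±16 points.

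**The case against.** The plan has several defences, and most of them narrow the point.

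- It does not rely on pooled testing alone. The COVID-19 section opens with a comparison of the pandemic and following periods. That stands, but the only measures named are the two above, and splitting them by period lets the cut-off float in each.
- Calibration is not absent. It is a selection criterion in both protocol texts, and calibration assessed by period would show a level shift. Neither text says it will be assessed that way.
- A reader might infer that the tool has one fixed cut-off. It has three triage categories, so more than one threshold, and ETAT+ criteria run on the same platform. That thresholds stay the same across periods is itself an inference, drawn from their being preselected with no rule for updating them.
- A reader might infer that the model is always trained on the periods it is tested in, so that no unseen period is predicted. The composition of the training data is never stated. The text is silent here, which does not establish the inference.
- A reader might infer that a surge would mean more missed sick children. The plan's expectation is possibly higher severity, which points at least as much to upward shifts, where sensitivity rises and specificity falls.
- The uniform shift is a simplification. A real change in case mix can also alter ranking, and the planned measures would detect that.

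Finally, this is an added analysis and does not touch the effectiveness outcome.

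**Conclusion.** The point holds as a gap in what the COVID-19 section commits to. The named measures assess discrimination only. A common shift in predicted risk or a change in baseline risk leaves both unchanged within a period. In the pooled example, a half-SD shift moves them by 0.007 in AUC and 1.3 percentage points in specificity, while sensitivity at the pooled cut-off differs between periods by 86.8 − 73.2 = 13.6 points.

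The invariance within a period is a property of the measures and needs no assumed AUC. The sizes do rest on assumptions: equal-variance normal scores, an AUC of 0.75 to 0.85, and shifts of 0.25 to 0.75 SD. The documents support none of these values directly, so the figures are illustrations and not predictions. Nor do the documents show that a failing model would be reported as consistent; they leave open whether any planned check would reveal the failure.

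**What to change.** In section 17, Additional Analyses due to the impact of COVID-19:

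1. Keep AUC and specificity at 80% sensitivity, labelled as measures of discrimination.
2. Add, separately for the pandemic and non-pandemic periods and with 95% confidence intervals: sensitivity and specificity at the frozen triage thresholds; the share of children in each triage category; and calibration intercept, calibration slope and observed/expected admissions.
3. Add a test that develops model and thresholds in one period and applies them unchanged to the other, then the reverse. State the training and test composition for each analysis. Refit on all data for the deployed model.

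The cost is SAP wording and analysis code, with no new data. The limit is precision. At the minimum sample, each half of one site has about 75 admissions (±9 points on 80% sensitivity), which is also below the 100 admissions implied by the plan's own rule for 10 predictors. The intervals must therefore be shown, and month-by-month hold-outs should be exploratory at most.
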